**3.15 Will HIV serostatus be evaluated specifically for the purpose of participation in this research study?**

\* No

If **Yes**, provide a justification:

[\[reviewer notes-\]](#)

**4.1** Select all recruitment methods to be used to identify potential subjects:  
Other Strategies: Described below

**4.2 Provide a detailed description of your recruitment methods, including identifying and initiating contact with participants:**

Children will be assessed during clinic visit to department of pediatric urology for nocturnal enuresis for eligibility in this study. Medical record and detailed history will be reviewed to ensure no confirmed neurological diagnosis or other known etiologies of nocturnal enuresis including bladder irritants or constipation which would make child ineligible. Routine urinalysis will be reviewed to rule out any urinary tract infection.

Note: Questions jump from 4.2 to 4.6 as questions 4.3-4.5 have been removed and the information is now captured in 4.1

[\[reviewer notes-\]](#)

**4.6 Are you requesting a waiver to document informed consent for any or all participants, for any or all procedures? (e.g., a verbal or computerized consent script will be used, but the subjects will not be required to sign a written informed consent document. *This is not a waiver to obtain consent.***

\* No

[\[reviewer notes-\]](#)

**4.7 Are you requesting a waiver to obtain informed consent or an alteration of the informed consent process for any of the following?**

\* Yes

**4.7.1 If Yes, select the reason(s) for your request:**

Medical record review for ONLY the identification of potential subjects

General Requirements: The Federal Policy **[45 CFR 46.116 (d)]** specifies in order for a waiver of consent to be approved, the request must meet four criteria. For each request, you will be asked to provide a justification addressing how each of these criterion is met.

**Medical record review for the identification of potential subjects:**

The research involves no more than minimal risk to the subjects;  
**[45 CFR 46.116 (d)(1)]**

We will only review medical records to identify potential subjects. We will not extract or record any information from the medical record. This review procedure imposes no physical or psychological risks to the patients. Therefore, we believe it has no more than minimal risk.

The waiver or alteration will not adversely affect the rights and welfare of the subjects;  
**[45 CFR 46.116 (d)(2)]**

The rights and welfare of these patients will not be negatively affected because this research team is comprised of pediatric urologists who already have legitimate access to the medical records by virtue of their clinical responsibilities.

The research could not practicably be carried out without the waiver or alteration;

**[45 CFR 46.116 (d)(3)]**

Whenever appropriate, the subjects will be provided with additional pertinent information after participation;

**[45 CFR 46.116 (d)(4)]**

It would not be practical to obtain the full consent of the urology patient without first reviewing the medical record. Medical record review is intended to determine whether or not the patient meets the eligibility criteria, which can not be used to replace the patient consent. A full consent will be conducted as described in this application.

We will not obtain any pertinent information from the medical record review.

**4.7.2 Under what circumstances (if any) will you obtain consent from some of these subjects?**

Under no circumstances will we obtain consent for medical record review. However, we will obtain a full consent from the patient's parent or guardian for the study to be performed.

[\[reviewer notes-\]](#)

**4.8 Are you requesting an exception to the requirement to obtain informed consent for research involving the evaluation of an 'emergency' procedure?**

**Note:** This exception allows research on life-threatening conditions for which available treatments are unproven or unsatisfactory and where it is not possible to obtain informed consent.

\* No

[\[reviewer notes-\]](#)

**4.9 Upload all consent documents for watermarking:**

Draft Consent Forms for editing:

Name	Modified Date
New Consent	5/13/2015 12:01 PM

Approved Consent Form(s):

Name Modified Date

[\[reviewer notes-\]](#)

**4.10 Will all potential adult subjects be capable of providing direct consent for study participation?**

\*

Not applicable

**Indicate why direct consent is not possible:**

Study participants will all be children < age 18 years old and therefore consent will be obtained from a parent or legal guardian.

[\[reviewer notes-\]](#)

**4.11 At what point will you obtain the informed consent of potential research subjects or their authorized representative?**

After performing certain of the screening procedures, but prior to performing any of the research interventions/interactions

**4.11.1 Address why you feel that it is acceptable to defer obtaining written informed consent until after the screening procedures have been performed.**

Our screening procedure only includes a review of patient medical record. We have a requested a waiver of consent for assessing medical record and provided the reasons for the waiver on section 4.7

**4.11.2 Taking into account the nature of the study and subject population, indicate how the research team will ensure that subjects have sufficient time to decide whether to participate in this study. In addition, describe the steps that will be taken to minimize the possibility of coercion or undue influence.**

The research study will be discussed in detail with the child's parent or guardian in the outpatient clinic by the pediatric urologist. If the parent is immediately interested in enrolling the child in the study, informed consent will take place during the clinic visit as will the providing of the TENS equipment will all necessary teaching on the use of the device. If the parent would like additional time to consider participation, we will wait for them to contact us at a later date. The intention for participation will always be initiated by the parent, thus we will make no attempts to call or email them if they do not contact us after the clinic visit.

[\[reviewer notes-\]](#)

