**Night-time voiding log:**

The subject/parents will be instructed to record a night-time voiding log specifying the number of incontinent episodes per night. This log is included in the IRB application. Subjects/parents will fill out the log for a two week period prior to foot stimulation to determine a baseline average of nocturnal enuresis episodes, during the two week foot stimulation period to measure any acute effect on nocturnal enuresis episodes and finally during the two weeks after stimulation to evaluate any post-stimulation residual benefit.

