**Neuromodulation:**

In the office to calibrate TENS device - skin surface electrodes will be attached to the bottom of one foot for electrical stimulation. The stimulator and electrodes are FDA-approved devices for TRANSCUTANEOUS ELECTRICAL NERVE STIMULATION (TENS) and are commercially available. The stimulation characteristics include a continuous frequency of 5 Hz, pulsewidth 0.2 ms, and intensity 2-4 times the threshold voltage required for inducing

toe twitching - or the intensity that the subject feels comfortable with. The subjects will also be instructed how to use the stimulator and where to attach the electrodes on the foot at the beginning of the study. The investigator will provide the stimulator and electrodes. The subjects will be asked to wear socks to prevent the electrodes from detachment and to stop the stimulation during walking or in any non-resting situation. Subjects will be provided a TENS device and disposable foot pads for two weeks of treatment. Subjects will be asked to use the stimulator for a MINIMUM of 60 minutes in the evening prior to bedtime at home for two weeks. They will be encouraged to use the stimulator for more time than the minimum as long as they accurately record the total duration. Stimulation will be performed during the second and third weeks of the study only.

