#### Questionnaire:

Subjects will complete the quality of life questionnaire attached to this application at the start of the study (prior to week 1) to establish a baseline, after the second week of treatment period (week 4 of study) to determine a treatment effect, and after the sixth week to determine any residual post-treatment effect.

The subjects can call or email the investigators anytime during the 6-week at-home test for questions or any problems encountered. At the end of the 6-week study, the subjects are asked to return the stimulator and night-time voiding log to the investigator's office.

Subjects who feel they are having a positive response to TENS treatment and would like to continue participation in the study for an additional 6 weeks may do so. We will ask that they continue to keep their logs and answer the questionnaires

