**5.9 Has or will a Federal Certificate of Confidentiality be obtained for this research study?**

\* No

**5.10 Question has been moved to 5.17****5.11 Question has been moved to 5.16**[\[reviewer notes~\]](#)**5.12 Does participation in this research study offer the potential for direct benefit to the research subjects?**

No - Describe the general benefits to society (e.g., increased knowledge; improved safety; better health; technological advancement) that may result from the conduct of this research study.

Describe the benefit:

The subject may not receive direct benefit from participation in this research study. Although the electrical stimulation may help with nocturnal enuresis, this benefit is not known or guaranteed. However, information learned from this study will help investigators learn how to better manage the conditions of nocturnal enuresis.

**5.13 Describe the data and safety monitoring plan associated with this study. If the research study involves multiple sites, the plan must address both a local and central review process.**

11. Drs. [name], [name] and [name] will be responsible for the data and safety monitoring.

2. After the ADDITIONAL 3 WEEKS OF ONGOING stimulation, parents will be called on the telephone by either [name] or [name] to inquire if any issues and assess the child's tolerability to continue treatments. All questions will be addressed as well. If no issues, the patient will continue the EXTENDED study and follow-up in clinic at the conclusion to submit their completed log and return the stimulation device. If during the monitoring telephone call an issue is detected, Drs. [name] or [name] will attempt to troubleshoot issues related to device usage over the telephone. A follow-up phone call will be scheduled on an as needed basis (2-3 days later) if any adjustments are made to the parents' technique of providing the stimulation or adjustments to the device settings. If at the monitoring phone call it is determined that the child is not reasonably tolerating the stimulation and/or they have developed concerning side effects, a prompt clinic appointment will be made to assess the child in person and remove them from the study.

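### Families who enrol at the clinic visit have the stimulator at home in both unstimulated windows, and the plan describes no record of its use on off nights

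*Combined protocol and SAP*

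**What the plan says.** The design is open-label and uncontrolled, and each child is compared with himself or herself (section 2.3). Three windows carry the comparison. For the first, section 2.6 (Night-time voiding log) says "Subjects/parents will fill out the log for a two week period prior to foot stimulation to determine a baseline average". The second is the stimulation fortnight, and the third is used "during the two weeks after stimulation to evaluate any post-stimulation residual benefit". Section 2.17 labels them weeks 1-2, 3-4 and 5-6.

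**Custody of the device.** When a parent agrees on the spot, section 4.11.2 says "informed consent will take place during the clinic visit as will the providing of the TENS equipment". Section 2.6 (Neuromodulation) has subjects "instructed how to use the stimulator and where to attach the electrodes on the foot at the beginning of the study". For return, section 2.6 (Questionnaire) says "At the end of the 6-week study, the subjects are asked to return the stimulator and night-time voiding log to the investigator's office". Children who continue into the extension instead "follow-up in clinic at the conclusion to submit their completed log and return the stimulation device" (section 5.13).

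**Control and recording of use.** The Neuromodulation text sets a 60-minute evening minimum for two weeks and adds: "They will be encouraged to use the stimulator for more time than the minimum as long as they accurately record the total duration". It supplies disposable pads for two weeks of treatment and confines stimulation to two named weeks. The log is described as a count of incontinent episodes per night. Section 2.7 answers No to research follow-up procedures, a category that includes phone calls. The one scheduled call, in section 5.13, belongs to the extension. Section 2.18 names the t-test and ANOVA and nothing further.

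**The concern.** With no control arm, the contrast depends on the off windows really being off. For same-day enrollers a working, calibrated device is in the house before the baseline log starts and stays there through the after-stimulation fortnight. All three windows run at home with no planned contact in between.

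The two possible errors point in opposite directions. Stimulation on baseline nights lowers the baseline count and hides part of any acute effect. Stimulation on after-period nights lowers that count and looks like an effect that persists. The residual-benefit question is the more exposed, because a family that has just seen drier nights has a reason to carry on. From the data the plan describes, an analyst could not separate a lasting effect from continued stimulation.

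**Working it through.** **Step 1: place custody against the windows (same-day enrollers).**

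| Window (section 2.17) | Intended state | Device at home? | Described record of use |
|---|---|---|---|
| Weeks 1-2 | off | yes, from the consent visit (4.11.2) | none described |
| Weeks 3-4 | on | yes | self-recorded duration (2.6) |
| Weeks 5-6 | off | yes, returned at the end of week 6 or later (2.6, 5.13) | none described |

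No dispensing point after baseline and no collection point after the stimulation weeks is described.

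**Step 2: check the definition of the windows.** Section 2.6 (Neuromodulation) puts stimulation in the second and third weeks only. Aim 2 in section 1.2 and section 2.17 put it in weeks 3-4, and the Questionnaire text ends treatment at week 4. A family that followed the Neuromodulation text would stimulate in week 2, inside the section 2.17 baseline. Weeks 1-2 and weeks 3-4 would then each hold one stimulated week of two, and without carry-over the expected contrast is 1/2 - 1/2 = 0. This requires no departure from instructions.

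**Step 3: illustrate the size of off-window use.** The documents give no effect size and no frequency of off-window use, so both are assumed. The 25 subjects in section 3.12 come from no power calculation, so there is no planned figure to reproduce.

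Set the unstimulated rate to 1 and the stimulated rate to 1 - r, with no carry-over. Let f be the share of nights stimulated in the off window concerned, with the other off window clean.

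- Observed acute reduction, baseline affected: 1 - (1 - r)/(1 - f·r)
- Apparent residual benefit, after-period affected, true value zero: f·r

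For r = 0.5 and f = 3/14:

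- Baseline rate: 1 - 0.107 = 0.893
- Acute reduction: 1 - 0.5/0.893 = 44%, against a true 50%
- False residual benefit: 0.5 × 3/14 = 10.7%, about 11%

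| Assumed true effect r | Nights stimulated | Observed acute reduction | False residual benefit |
|---|---|---|---|
| 50% | 3 of 14 | 44% | 11% |
| 50% | 7 of 14 | 33% | 25% |
| 30% | 3 of 14 | 25% | 6% |
| 30% | 7 of 14 | 18% | 15% |

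The 30% rows use the same formulas. For 3 of 14 nights, 1 - 0.7/(1 - 0.064) = 25% and 0.3 × 3/14 = 6%. For 7 of 14 nights, 1 - 0.7/0.85 = 18% and 0.3 × 0.5 = 15%.

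The figures are averages over the group. If only some families stimulate off-window, f is the group-wide share of nights. The 7-of-14 rows are an outer case: they need seven sessions beyond the 14 planned, from pads supplied for two weeks, and the plan gives neither pad numbers nor a rule on reuse.

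**The case against.** The strongest reply is that the plan does set limits. It names the weeks of stimulation and excludes others, it asks families to record duration accurately, and it supplies pads for two weeks only. Responders also have an approved route to six more weeks, which weakens the motive for unsanctioned use. Nothing in the documents suggests that off-window use is common.

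Much of this stands, and it rules out several stronger readings:

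- A reader might infer that nothing in the plan could reveal off-window use. That goes too far. Duration is recorded in some form, and the log is an uploaded attachment that is not shown, so a use column cannot be ruled out.
- A reader might take the encouragement to exceed the minimum as leave to stimulate at any time. In context it concerns longer evening sessions within two weeks of use, and the same section restricts the weeks.
- A reader might apply same-day handover to every family. Section 4.11.2 states it only for parents who agree at once and gives no equipment handover time for those who decide later.

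What remains is a lack of verification. The duration request is attached to treatment use, no pad count is described, and a pad supply does not control when pads are used. The extension does not remove the motive in weeks 5-6, since section 2.11 gives a total of 6 to 12 weeks, which suggests that it follows the core six.

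**Conclusion.** The point holds as a gap in recording and in the analysis plan. For same-day enrollers the device is available in both off windows, and the described procedures would leave off-night use unrecorded and unaddressed in the analysis. The size is unknown. Under the assumed 50% effect, no carry-over and 3 of 14 nights, the distortion is modest: 50% becomes 44% for the acute contrast, and a false residual benefit of about 11% appears. Baseline use works against finding an effect, so false benefit arises only in the after-period comparison.

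The documents do not support concluding that such use will occur, or that the residual-benefit result is invalid. The disagreement over stimulation weeks is the firmer defect, because it is written in the text and could remove the contrast among families who comply. It has to be settled before an off window can be defined.

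**What to change.** 1. Reconcile the stimulation weeks across section 1.2 (Aim 2), section 2.6 and section 2.17.
2. In section 2.6, add minutes of stimulation to the nightly log for all 42 nights (6 × 7), with 0 entered on off nights.
3. In sections 2.6 and 4.11.2, keep calibration and training at enrolment, but release the home pads at the start of the reconciled stimulation window, for example by mail on a fixed date. A fixed date avoids having to confirm that the baseline log is complete. State the handover for families who decide later.
4. Count leftover pads when the device is returned. Early return of the stimulator is not needed and would mean re-issuing it for the extension.
5. In section 2.18, report off-window use by window, and give a sensitivity analysis of the baseline and after-stimulation rates without those nights. Use episodes per night there, because the section 2.17 count per fortnight is not comparable once nights are dropped.

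The cost is one more log item for families, one mailing per child and an IRB modification. The limitation is that use is still self-reported; the pad count is only a rough cross-check.

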**T3.1**

**Why do you feel that all aspects of this research study, including screening and follow-up, involve no more than minimal risk to the research subjects?**

Trans-cutaneous Electrical Nerve Stimulation (TENS) devices are FDA approved and commercially available to treat a variety of clinical conditions including pain (migraines, musculoskeletal pain and labor pain). The only reported side-effects are local irritation from electrode pads and minor cramping of stimulated muscles. Many studies have evaluated the use of TENS devices for parasacral neuromodulation in children with no serious adverse events reported.

The voltage used for the TENS device will be only as high as is required to stimulate an involuntary muscle contraction of at least two toes. In various trials in adults this voltage very rarely corresponds to any actual discomfort to the patient. If during the trial stimulation at the time of enrollment in the office, the child demonstrates an intolerance to this stimulation due to discomfort, he/she will be excluded from the study.

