**2.17 What are the main outcome variables that will be evaluated in this study?**

1) Number of night-time incontinent episodes per two week period comparing baseline number of voids (first two weeks of study), number during two-week stimulation period (weeks 3-4), and number during two-week after-stimulation period (weeks 5-6).

2) Subjective quality of life measures as recorded by validated quality of life questionnaire prior to study start, after week 4 and after week 6 to evaluate for any differences.

3) For the subjects who continue participation for an additional 6 weeks, we hope to prove long-term efficacy and sustainability in symptom relief, and to ensure no unanticipated adverse outcomes with continued usage

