**3.14 Exclusion Criteria: List the specific criteria for exclusion of potential subjects from participation.**

1. Children with known neurological disorders which may be contributing to nocturnal enuresis episodes

2. Children found through history to have significant behavioral causes of nocturnal enuresis including consumption of excessive fluids or known bladder irritants

3. Children with chronic constipation who are non-compliant with previous pharmacologic efforts to treat.

4. Children who are not adequately potty trained

5. Children with significant daytime symptoms of overactive bladder including frequency, urgency, and daytime incontinence

5. Children who do not tolerate initial stimulation training session in the urology clinic upon enrollment

6. Children with any implantable medical devices such as a pacemaker will be excluded from the study

Note: Any patient currently taking medication such as an anti-muscarinic or a tricyclic antidepressant for overactive bladder at time of enrollment will be eligible to participate and will be continued on their usual medication and dosage throughout the study.

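### Device teaching and the only staff-observed toe check come before baseline, and nothing scheduled in the six-week core phase records whether home stimulation was effectively delivered

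*Combined protocol and SAP*

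**What the plan says.** Teaching takes place once, in clinic. Section 2.6 (Neuromodulation) says subjects are shown "how to use the stimulator and where to attach the electrodes on the foot at the beginning of the study". Under section 4.11.2, when the parent agrees at once, consent is taken at that clinic visit, "as will the providing of the TENS equipment will all necessary teaching on the use of the device". Section T3.1 describes tolerance being judged "If during the trial stimulation at the time of enrollment in the office", and section 3.14 excludes "Children who do not tolerate initial stimulation training session in the urology clinic upon enrollment". In TENS Unit Training (2.6), the parents raise the voltage until at least two toes, including the great toe, contract, and stimulation then runs for five minutes.

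Baseline comes next: "Subjects/parents will fill out the log for a two week period prior to foot stimulation". Section 2.17 then defines outcome 1 by calendar window, including the "number during two-week stimulation period (weeks 3-4" window. Section 1.2 (Aim 2) also gives the third and fourth weeks, whereas Neuromodulation in 2.6 gives the second and third.

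Section 2.7 answers No to follow-up procedures for research, a category that includes phone calls. The one scheduled call that deals with technique is in section 5.13, item 2: "After the ADDITIONAL 3 WEEKS OF ONGOING stimulation, parents will be called on the telephone". That is in the optional extension. Families may contact the investigators at any time in the core phase (2.6, Questionnaire) and receive a user manual. The log is described as counting episodes per night, and families also record duration of use. The analysis plan in 2.18 names the t-test and ANOVA and nothing more.

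**The concern.** Each family has to place two pads at particular sites, connect the leads and find a working setting, alone, one or two weeks after being shown how. If the pads are misplaced or the session is otherwise ineffective, the log as described looks the same as for an effective session: a duration and a count of wet episodes. Nothing in 2.17 or 2.18 would separate that child from the others.

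Section 3.12 says the pilot is meant to find out whether foot stimulation has any effect. A null result would then have two explanations, that stimulation does not help or that it was not delivered, and the data described could not distinguish them. The one technique call in 5.13 cannot help with this, because it falls after the core comparison is complete.

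**Working it through.** **1. Plan's own figure.** Section 3.12 sets 25 subjects and says the variation is unknown. It gives no SD, effect size, alpha or power, so there is no calculation to reproduce.

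**2. Gap from teaching to first home session.** With teaching just before week 1, gap = (first stimulation week − 1) × 7 days.
- Weeks 3–4 (1.2, 2.17, consistent with the two-week baseline log in 2.6): (3 − 1) × 7 = 14 days.
- Weeks 2–3 (2.6, Neuromodulation): (2 − 1) × 7 = 7 days.

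There is an unsupervised gap under either timetable.

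**3. Scheduled staff checks of delivery.** Core six weeks: 0 (2.6, 2.7). Extension: 1 call (5.13, item 2).

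**4. What a family is asked to record.** Episodes (2.6, Night-time voiding log) and duration (2.6, Neuromodulation). No section asks for toe response, pad attachment or intensity. The log form is an attachment that was not available for review, so it may hold more fields.

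**5. Illustration of dilution.** All inputs except n = 25 are assumptions. The test is a paired two-sided t-test at 5%, using the noncentral t with 24 degrees of freedom (critical value 2.064) and noncentrality 5 × d, since √25 = 5. Power is 80% at d = 0.584 SD of within-child change. A share f of children has ineffective delivery and loses a fraction s of the change:

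d_eff = d(1 − s·f) / √(1 + f(1 − f)(s·d)²)

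*Undelivered children do not change (s = 1):*
- f = 10%: 0.526 / √1.031 = 0.518, power 70%
- f = 20%: 0.467 / √1.055 = 0.455, power 59%
- f = 30%: 0.409 / √1.072 = 0.395, power 47%

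*Half of the change is nonspecific and occurs anyway (s = 0.5):*
- f = 10%: 0.555 / √1.008 = 0.553, power 76%
- f = 20%: 0.526 / √1.014 = 0.522, power 71%
- f = 30%: 0.496 / √1.018 = 0.492, power 66%

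The documents give no value for f or s. Section 3.12 also allows recruitment to stop early, so 25 is taken here as the final number.

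**The case against.** The training is specific and hands-on. The parents find the toe response themselves in clinic, the frequency is preprogrammed, a manual is supplied and help is available on request. Absent toe movement is a visible sign that they have been taught to look for. Section 5.7 discontinues children who cannot follow procedures and accepts occasional electrode detachment. This is a pilot, and some loss of delivery is part of home use. All of that stands, and it lowers the likely failure rate. It does not supply a record: the manual and the phone line help a family that notices a problem, and the examples in 5.7 (intolerance, incomplete logs or questionnaires) would not catch a completed log from ineffective sessions.

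A reader might also infer four stronger points that the documents do not support:
- **That stimulation which never worked is counted as treatment.** No section says so. It follows only by inference from the absence of any delivery rule in 2.17 and 2.18.
- **That a session without toe movement is a session without stimulation.** Section 2.6 also allows an intensity the child finds comfortable, while 5.1.1 ties the voltage to toe movement. Until those are reconciled, such a session may comply with the plan.
- **That power would fall to 47%.** This needs an unsourced 30% failure share and no change at all in undelivered children. In an open-label before-after comparison (2.3), such children can still improve through expectation or regression to the mean.
- **That children with failed delivery would not enter the extension.** Entry depends on feeling a response, which unblinded families may report without effective delivery.

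**Conclusion.** The point holds as a gap in measuring delivery. The only planned teaching and staff-observed toe check precede the baseline log. The first home session comes about 14 or about 7 days later, depending on which section is followed. No core-phase contact or described record shows whether stimulation was effective. Ineffective sessions would enter the stimulation window unrecognised, would tend to pull a true stimulation effect toward zero, and would leave a null pilot unable to separate lack of effect from lack of delivery.

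The size is not derivable from the plan. With 10% to 30% undelivered, the illustration runs from 70% down to 47% power in the extreme case and from about 76% down to 66% if half the change is nonspecific. It shows direction and plausible range, and is not an estimate for this trial. The conclusion about records is conditional on the log form having no delivery fields beyond those described.

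**What to change.** 1. Reconcile the stimulation weeks in 1.2, 2.6 and 2.17, and the intensity statements in 2.6 (Neuromodulation) and 5.1.1. This review does not choose between them.
2. For the stimulation weeks, add nightly log fields if they are not already on the form: stimulation done, duration, pads stayed attached, and toe movement seen (yes/no). The last is descriptive and does not define compliance.
3. Add to 2.6 one brief scripted call by existing study staff at the first home session, to go through placement and record the actual start date. Add a similar brief call at the start of the baseline log. A call in the stimulation window alone would add staff attention to one side of an unblinded before-after comparison. Update the answer in 2.7.
4. In 2.18, report the number of evenings with recorded delivery per child beside outcome 1. Keep all children in the main comparison, and use delivery only in a supportive analysis.

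**Cost:** about 50 short calls (25 children × 2), a few log fields and a minor amendment. The calls take staff time, and delivery remains parent-reported, so pad position is still not directly verified.
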